3.2.3 Inclusion Criteria

Subjects satisfying the following criteria will be considered eligible for enrollment in this study:

1. Primary laparoscopic or open procedure (thoracic, urologic or ENT) where at least one vessel is planned to be transected by the ENSEAL X1 device per the IFU;
2. Willingness to give consent and comply with all study-related evaluations and treatment schedule; and
3. At least 18 years of age.

3.2.4 Exclusion Criteria

Subjects meeting the following criteria will be considered ineligible for enrollment in this study:

1. Physical or psychological condition which would impair study participation; or
2. Enrollment in a concurrent interventional clinical study that could impact the study endpoints.

3.2.5 Removal of Subjects from Study

A subject has the right to withdraw from the study at any time for any reason without prejudice to his/her future medical care by the physician or the institution. Should a subject (or subject's legally authorized guardian/representative) decide to withdraw, 1) all data collected up to the point of withdrawal will be considered for analysis; and 2) all efforts will be made to collect and report the final visit observations as thoroughly and timely as possible. Participation may be terminated prior to completing the study for any of the reasons listed below (reasons that do not fit the categories below will be documented as "other").

Adverse Event

When the subject experiences an AE and the Investigator or Medical Monitor believes it is in the best interest of the subject to discontinue participation in the study, the subject will be withdrawn from the study.

Lost to follow-up

When contact with the subject has been lost without completing a final contact assessment, and every attempt to contact the subject has failed, the subject will be considered lost to follow-up. All attempts to contact the subject requesting his/her return for the final visit must be documented.

Withdrawal of consent

Any method of contact with the subject (or subject's legally authorized guardian/representative) in which he/she state they no longer want to participate in the study specific activities constitutes withdrawal of consent for participation in the study. When possible, the reason for withdrawal will be documented.

Site Termination or Study Termination

A study site or the entire study may be terminated. When this occurs, all subjects currently enrolled at the site will be withdrawn and documented as early terminations. Reasons for site or study termination may include, but are not limited to the following:

- Administrative concerns (e.g., inadequate subject enrollment, Investigator/institution non-compliance, change of business strategy, etc.);
- Safety Issues, including those due to non-compliance, which substantially affect the risk to benefit ratio of the study subjects at a site or for the study as a whole; or
- Regulatory Body Mandate(s).

The Investigator has the right to terminate the subject's participation at any time. Should this be necessary, procedures for termination will be provided by the Sponsor.

Death

- When possible, the cause of death will be documented.

Other (which may include)

- Investigator recommendation.

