	subjects will be followed post-operatively through discharge and again at 28 days (\pm 14 days) post-surgery; therefore, from the surgery date to study exit, the duration will be approximately 6 weeks.
Number of Subjects:	A minimum of 105 subjects enrolled (maximum of 120 subjects enrolled) will be included in the study from up to 12 surgery centers globally with the following procedure targets: 
 • A minimum of 35 subjects enrolled to a maximum of 40 subjects enrolled for thoracic procedures (e.g., lung resections [branches, no pulmonary artery/pulmonary vein {PA/PV}]); • A minimum of 35 subjects enrolled to a maximum of 40 subjects enrolled for urologic procedures (e.g., nephrectomy); and • A minimum of 35 subjects enrolled to a maximum of 40 subjects enrolled for ENT procedures (e.g., thyroidectomy, tonsillectomy, parotidectomy, radical neck).
Criteria for Inclusion:	Subjects satisfying the following criteria will be considered eligible for enrollment in this study: 
 1. Primary laparoscopic or open procedure (thoracic, urologic, or ENT) where at least one vessel is planned to be transected by the ENSEAL X1 device per the IFU; 2. Willingness to give consent and comply with all study-related evaluations and visit schedule; and 3. At least 18 years of age.
Criteria for Exclusion:	Subjects meeting any of the following criteria will be considered ineligible for enrollment in this study: 
 1. Physical or psychological condition which would impair study participation; or 2. Enrollment in a concurrent interventional clinical study that could impact the study endpoints.
Test Product:	ENSEAL® X1 Curved Jaw Tissue Sealer (Product Codes: NSLX125C, NSLX137C, or NSLX145C) and Generator G11 (GEN11).
Reference Therapy/Product:	No comparator product is being used in this study.
Duration of Treatment:	Subjects will be exposed to the ENSEAL X1 device during the procedure and while the device is used as indicated in the IFU. The device nor any device components remain in the patient after use.
Criteria for Evaluation:	The primary performance endpoint will be: 
 • The number and percentage of vessels where hemostasis is achieved (\leq Grade 3) per the grading scale below: 
 ○ Grade 1: no bleeding at transection site;

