3.6.3 Visit 3 – Post-procedure Follow-up Visit

After the date of surgery, subjects will have a follow-up visit approximately 28 days (\pm 14 days) later. This visit can be either an office visit or a telephone follow-up. Data to be collected is defined in Section 3.5.

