6.4 REPORTING PROCEDURES FOR ADVERSE EVENTS

6.4.1 Recording Adverse Events

The Investigator will record all AEs (both AEs and SAEs) considered attributable (relationship of possible, probable, causal relationship) to the study procedure or the ENSEAL X1 or GEN11 devices in the source documents and eCRF.

Standard medical terminology should be used when recording AEs. In addition, the following information should be recorded:

- Onset date;
- Resolution date or date of death;
- Severity of the event;
- Indication of whether the event is serious;
- Relationship of AE to the study devices;
- Relationship of AE to the study procedure;
- Action taken;

- Event status; and
- Was AE anticipated or not (only for SAEs).

Data related to AEs will be collected until the event resolution, or until the event is considered stable, or until all attempts to determine the resolution of the event are exhausted. All AEs that are unresolved at study completion (or at the last visit completed for early withdrawal subjects) will be recorded as ongoing at study end.

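### Final safety contact is promised only to subjects who choose to withdraw, not to already-exposed subjects withdrawn through site or study termination or after an AE

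*Protocol*

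**What the plan says.** **Termination.** Protocol 3.2.5 on closure of a site or of the study: "When this occurs, all subjects currently enrolled at the site will be withdrawn and documented as early terminations". Among the listed reasons is "Safety Issues, including those due to non-compliance, which substantially affect the risk to benefit ratio of the study subjects".

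**Adverse event.** The same section withdraws a subject who has an AE when "the Investigator or Medical Monitor believes it is in the best interest of the subject to discontinue participation in the study".

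**Final data after withdrawal.** Where a subject or representative decides to withdraw, 3.2.5 promises that "all efforts will be made to collect and report the final visit observations as thoroughly and timely as possible". For loss to follow-up, it requires contact attempts to be documented. It states nothing similar for AE withdrawal or for site or study termination. For termination of participation by the investigator, it refers to sponsor procedures that the protocol does not contain.

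**Exposure.** Protocol 3.1 counts a subject as enrolled once use of ENSEAL X1 on a vessel has been attempted. The synopsis (Duration of Treatment) adds: "The device nor any device components remain in the patient after use".

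**Remaining follow-up.** Protocol 3.1 has all enrolled subjects followed to discharge and again at 28 ± 14 days. Of that last visit, 3.6.3 says: "This visit can be either an office visit or a telephone follow-up".

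**Recorded AEs.** Protocol 6.4.1 has AE data collected to resolution, to a stable state, or until attempts to learn the outcome run out. Its next sentence says that AEs unresolved at study completion ("or at the last visit completed for early withdrawal subjects) will be recorded as ongoing at study end".

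**Analysis.** Protocol 3.2.6 rules out replacement. Protocol 5.9.6 and SAP 8.7 use observed data without imputation. The footnote to SAP Table 14, whose format Tables 15 to 19 share, divides by all subjects in the column.

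**The concern.** In many trials, withdrawing a subject stops further exposure. Here it cannot, because everyone enrolled has already had the device used or attempted. After discharge, the Schedule of Events leaves only concomitant medications, re-operations, related AEs and completion status. Ending participation at that stage protects no one from the device and gives up the remaining safety information.

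The protocol is also lopsided. It commits to pursuing final data from people who choose to leave, but states no such effort for people removed by the sponsor or the investigator. If a closure is prompted by safety, recently operated subjects at that site are the ones whose later course most needs to be known. They would remain in the denominator of the safety endpoint (device-related AEs) while any new related event before Visit 3 could go unseen.

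**Working it through.** **1. Who is affected.** Combining 3.1, 3.2.5 and the Schedule of Events, the affected subjects are those currently enrolled who have not completed Visit 3. Subjects who have completed it are untouched. The primary and secondary performance endpoints are collected intra-operatively (Protocol 5.3) and are also untouched.

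**2. What can be lost on each route.**
- *Site or study termination:* any related AE or re-operation arising after withdrawal and before Visit 3, which falls between Day 14 and Day 42.
- *AE withdrawal:* less. Only related AEs are collected (Protocol 6.0), and Table 14 counts each subject once for a given AE. A subject withdrawn for a collected AE is already in its row for subjects with at least one AE. What could be missed is a later, different event, such as a device-related AE after a purely procedure-related one.

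**3. The plan's own safety figures.** Protocol 5.7 gives 88.0% and an upper limit below 3.5%, from n = 105 and a 2% event.
- Chance of at least one event: 1 − 0.98^105 = 0.8801.
- Exact two-sided 95% upper limit with no events: 1 − 0.025^(1/105) = 3.45%.

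Both reproduce. Both assume complete ascertainment in all 105 subjects.

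**4. Illustration.** The documents give neither an expected dropout nor enrollment per site, so the number lost, m, is an assumption. With n = 105 − m, the table treats each lost subject as giving no safety data at all. The last column keeps all 105 in the denominator, as Tables 14 to 19 do.

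| m (assumed) | n | 1 − 0.98^n | 1 − 0.025^(1/n) | Expected reading of a true 2%: 2% × n/105 |
|---|---|---|---|---|
| 0 | 105 | 88.0% | 3.45% | 2.00% |
| 5 | 100 | 86.7% | 3.62% | 1.90% |
| 9 (about one site: 105/12 = 8.75) | 96 | 85.6% | 3.77% | 1.83% |
| 15 | 90 | 83.8% | 4.02% | 1.71% |
| 35 (the size of one procedure group) | 70 | 75.7% | 5.13% | 1.33% |

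For a given m these rows are upper bounds on the loss when withdrawal is unrelated to risk, because intra-operative and pre-withdrawal AEs are kept. If only a fraction f of events would arise after withdrawal, the expected reading is 2% × (1 − m·f/105). That equals the table at f = 1 and 2.00% at f = 0. The documents do not give f.

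**5. The two sentences in 6.4.1.** The first follows a recorded AE to its outcome. The second fixes the status of an unresolved AE at the last completed visit for an early-withdrawal subject. Neither covers new events after withdrawal, and the text does not say which governs a recorded AE in a subject withdrawn under 3.2.5.

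**The case against.** The case against making much of this is substantial. The study is descriptive, single-arm and post-market, uses a cleared device and tests no hypothesis. Harm requires a closure, or a discretionary AE withdrawal, inside a short window. A closure may also follow a regulatory mandate or site non-compliance, where continued contact through the site may not be possible. Enrollment can reach 120, and losing 15 of 120 still leaves 105, the number behind the plan's figures. All of this stands as a limit on materiality. The extra enrollment is only a partial answer: it is not tied to losses, and 3.2.6 bars replacement.

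Some stronger readings are tempting but unsupported:

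- *Any AE ends participation.* It does not; 3.2.5 requires a best-interest judgement.
- *Safety follow-up stops outright and AE outcomes are never learned.* Section 6.4.1 provides for following recorded AEs to resolution or stability. What is missing is a stated final contact for new events, together with a conflict over unresolved ones.
- *The safety endpoint is biased downwards by a known amount.* The loss counts are assumptions, earlier AEs are kept, and on the AE route the subject is usually already counted.
- *The Adverse Event category should be deleted, or follow-up at a closed site made unconditional.* The first would override a judgement the protocol assigns to the Investigator or Medical Monitor. The second ignores mandates and non-compliance.

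**Conclusion.** The point holds as a gap in safety ascertainment that is cheap to close. The termination rule is an explicit instruction to withdraw exposed subjects, and no final-visit effort is stated for them or for subjects withdrawn after an AE. With fixed denominators, no replacement and no imputation, missed events can only lower the reported incidence.

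The size is not determined by the documents. It depends on how many subjects are short of Visit 3 when they are withdrawn and on how many related events would arise after that. Under the assumed losses of 5 to 15 subjects, the upper-bound effect is a detection probability of 86.7% to 83.8% instead of 88.0%, and a zero-event limit of 3.62% to 4.02% instead of 3.45%. If the subjects cut off are at higher risk, as is plausible after a safety closure, the understatement could exceed what simple counts suggest, but nothing in the documents lets that be quantified. The conclusions on hemostasis are not affected.

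**What to change.** In Protocol 3.2.5, extend the existing commitment to obtain final-visit observations to every discontinuation route: AE, investigator decision, and site or study termination. State that subjects already exposed receive a final safety contact through Visit 3, by telephone if needed, unless consent is withdrawn or a regulatory mandate or site non-compliance prevents it. The Adverse Event category can stay as it is.

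Reconcile 3.2.5 with 6.4.1 by stating which rule applies to an unresolved AE in a subject withdrawn early, and reconcile both with the follow-up promised to all enrolled subjects in 3.1.

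The cost is a wording amendment, about one telephone contact per affected subject, and a short delay in closing a terminated site: at most six weeks after its last surgery, since Visit 3 closes at Day 42.

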3.2.6 Subject Replacement in Study

Subjects who withdraw or are terminated early from the study will not be replaced.

3.3 STUDY PROCEDURES

3.3.1 Procedure Description

Elective thoracic, urologic, and ENT procedures where ENSEAL X1 is indicated for use will be performed per the institution's SOC. Only the principal investigator or sub-Investigator can use the device during the vessel transections.

3.3.2 Identity of Study Products

The ENSEAL X1 and the GEN11 are the study products for this study.

3.3.2.1 Device Description

ENSEAL X1

The ENSEAL X1 instrument is a sterile, single-patient-use surgical instrument to coagulate and transect vessels up to and including 7 mm in diameter, tissue and/or vascular bundles. This device is to be used for soft tissue only. The instrument consists of a grip housing assembly, a rotating shaft, a moveable jaw, and a knife. The instrument shaft can be rotated 360° to facilitate visualization and enable easy access to targeted tissue. The jaws are in a normally-opened position and can be partially or fully closed by squeezing the closing handle. The jaws are designed for grasping and holding targeted tissue when clamped. The ENSEAL X1 has separate seal and cut capabilities. The lower jaw of the ENSEAL X1 can be used in the open or closed position to deliver energy based on the electrode configuration and jaw design. Bipolar energy is delivered when the SEAL button on the device or the MIN foot pedal is pressed. Pressing the CUT button advances the knife the length of the jaws to cut the targeted tissue. The power cord is permanently attached to the device and connects the instrument to the generator. The ENSEAL X1 instrument is designed for use exclusively with the GEN11 software version 2016-1 or later, packaged separately.

GEN11

The GEN11 device supplies energy to the HARMONIC and ENSEAL surgical instruments. The generator uses a touchscreen display interface and has a unique receptacle port that accepts either a HARMONIC or an ENSEAL instrument. Connectors (HGA11 for HARMONIC and EGA11 for ENSEAL) are used to enable the generator to power legacy instruments.

3.3.2.2 Indications

ENSEAL X1

The ENSEAL X1 are bipolar electrosurgical instruments for use with an electrosurgical generator. They are intended for use during open or laparoscopic surgical procedures to cut and seal vessels, and to cut, grasp and dissect tissue during surgery.

Indications for use include open and laparoscopic general, gynecological, urologic, thoracic, and ENT surgical procedures or any procedure where vessel ligation (cutting and sealing), tissue grasping, dissection, and division of vessels, lymphatics, and tissue bundles is performed (e.g. bowel resections, hysterectomies, gall bladder procedures, Nissen Fundoplication, adhesiolysis, and oophorectomies). The devices can be used on vessels up to and including 7 mm and bundles as large as will fit in the jaws of the instruments.

The ENSEAL X1 have not been shown to be effective for tubal sterilization or tubal coagulation for sterilization procedures.

GEN11

The GEN11 provides radiofrequency power to drive ENSEAL electrosurgical instruments that are used during open or laparoscopic general and gynecological surgery to cut and seal vessels and to cut, grasp, and dissect tissues. In addition, the generator provides power to drive HARMONIC ultrasonic surgical instruments that are indicated for soft tissue incisions when bleeding control and minimal thermal injury are desired.

ENSEAL and HARMONIC instruments, when used with the GEN11, have not been shown to be effective for sterilization procedures or tubal coagulation.

3.3.2.3 *Contraindications*

ENSEAL X1

The efficacy of the ENSEAL X1 for the indication of contraceptive tubal coagulation (permanent female sterilization) has not been evaluated and is unknown. The design of the ENSEAL tissue sealing device is significantly different from bipolar designs that are marketed for the indication of contraceptive tubal coagulation. The design differences may affect the efficacy of the procedure and failure rates may not be comparable.

GEN11

The use of the GEN11 and the attached instruments are contraindicated when, in the judgement of the physician, radiofrequency or ultrasonic surgery would be contrary to the best interest of the patient. The instruments are not indicated for incising bone.

3.3.2.4 *Labeling of Study Products*

The ENSEAL X1 has received 510(k) clearance in the United States by the Food and Drug Administration (FDA), has CE Mark in the European Union and United Kingdom and has clearance in Japan by the Pharmaceuticals and Medical Devices Agency (PMDA). The GEN11 has clearance for distribution in the United States by the FDA, has CE mark in the European Union and United Kingdom and has clearance in Japan by the PMDA. The study devices will use the cleared labeling. The Sponsor requires no additional labeling in this study.

3.3.2.5 *Accountability of Study Products*

The ENSEAL X1 may be provided to the participating institutions. The GEN11 (including footswitches) may be loaned to any institution in the study. Each institution not provided with ENSEAL X1 will use devices acquired through normal procurement process. If institutions are provided ENSEAL X1, the devices will be tracked using shipping receipts and device accountability logs and all device returns will be managed by contacting EES. Devices provided for the study must be kept in a secure area and used only for treating subjects participating in the study, in accordance with the protocol. If applicable, the study device inventory must be available for periodic inspection/verification.

3.3.3 *Prior and Concomitant Therapy*

Subjects will be assessed for certain prior medication therapy used up to 30 days prior to surgery. These medications include aspirin, antiplatelet agents, nonsteroidal anti-inflammatory drugs, and anticoagulants. Review will occur during Visit 1 (Screening Visit) and Visit 2 (Procedure Visit).

Subjects will be assessed for occurrence of pre-surgical radiation/chemotherapy used up to 90 days prior to surgery. Review will occur during Visit 1 (Screening Visit) and Visit 2 (Procedure Visit).

Subjects may continue with their current medical care while in the study and the following medications will be collected for this study:

- Certain prior medication therapy used up to 30 days prior to surgery (listed above); and
- Any medications administered during the study due to a device-related or procedure related AE.

3.4 STUDY VARIABLES

Specific variables assessed in the study are provided in the following sections. Refer to Section 3.5 Schedule of Events for the time when the study variables will be collected throughout the course of the study.

3.4.1 Demographic and Baseline Characteristics

The following will be collected preoperatively:

- Age (years);
- Gender;
- Race;
- Ethnicity;
- Pregnancy test result, if taken as per standard of care;
- American Society of Anesthesiologists Physical Status Classification System (ASA) score;
- Occurrence and location of cancer, if applicable;
- Review and collection of relevant medical history, surgical history, and the following:
 - Surgical procedure to be conducted, including primary indication for surgery; and
 - Smoking history (current smoking status, if stopped, length of time [months and years]).

3.4.2 Surgical Variables

The following variables will be recorded preoperatively, intraoperatively, or postoperatively:

- Date/time of hospital admission;
- Body weight (kg or lbs; no shoes);
- Body height (cm or in; no shoes);
- Procedure duration, defined as first skin incision to final skin closure;
- Did vessel skeletonization occur (Yes/No; if Yes, describe vessel skeletonized and device used)?;
- Was there presence of inflamed tissue, calcified tissues/vessels, atherosclerotic tissue, fibrotic tissue, or presence of adhesions intraoperatively, if applicable (Yes/No; if Yes, describe the tissue along with location)?;
- Were adhesions removed or divided by ENSEAL X1 (Yes/No; if Yes, describe adhesions along with location and complete 5-point scale)?;
- Were lymphatics and tissue bundles divided by ENSEAL X1 (Yes/No; if Yes, describe lymphatics and tissue bundles along with location and complete 5-point scale)?;
- Was ENSEAL X1 used for grasping tissue, tissue cutting, or tissue dissection (Yes/No; if Yes, describe activity along with location and complete 5-point scale)?;

- Conversion to open with reason, if applicable;
- Volume of estimated intra-operative blood loss;
- Use of any other energy device (monopolar, traditional bipolar, advanced bipolar, ultrasonic) in primary procedure (type, name, and number of device and reason for use), if applicable;
- Name, product code, and number of Ethicon trocars used with ENSEAL X1; if applicable;
- Type and name of trocar used with ENSEAL X1 device, if applicable;
- Was there prophylactic use of clips as standard of surgical care before vessel transection (Yes/No; if Yes, name vessel transected, and number of clips prophylactically applied);
- For each vessel transected with ENSEAL X1:
 - Name of each vessel;
 - Hemostasis grading scale assessment (1-4);
 - Surgeon determination of diameter size range (< 3 mm, 3 to 5 mm, and > 5 to 7 mm);
 - Image captured where the vessel is perpendicular and below the open jaw of the ENSEAL X1 device;
 - For every Grade 3 vessel transection:
 - Compression used as a mild intervention, if applicable (Yes/No);
 - Touch-ups with a monopolar device, if applicable (Yes/No; if Yes, record number of touch-ups);
 - Touch-ups with a bipolar device, if applicable (Yes/No; if Yes, record number of touch-ups);
 - Touch-ups with ENSEAL X1 (Yes/No; if Yes, record number of touch-ups);
 - For every Grade 4 vessel transection intervention:
 - Type, name, and number of times used for each additional hemostatic measure used along with a description of why it was considered Grade 4;
- Occurrence of blood transfusion, if applicable (record the total required units of blood and rationale);
- Concomitant procedures, if applicable (defined as any medical or surgical procedure beyond activities associated with primary study procedure). If a concomitant procedure requires vessel transection by ENSEAL X1, each vessel transected will have the same information collected as stated above for vessel transections, but these will not be included as part of the primary endpoint;
- Concomitant medication usage associated with device-related or procedure-related AEs and specific drugs used up to 30 days prior to surgery (aspirin, antiplatelet agents, nonsteroidal anti-inflammatory drugs, anticoagulants) and 90 days prior to surgery (pre-surgical radiation/chemotherapy); and

- Date/time of hospital discharge.

